Recent studies have explored the metabolic and functional benefits of high-intensity interval training (HIIT), which alternates short bursts of high-intensity effort with recovery periods (Coates et al., 2023). Compared to continuous moderate-intensity training, HIIT has been shown to improve maximal oxygen uptake and induce muscular adaptations more rapidly and with lower total training volume (Oliveira et al., 2024; Ramos et al., 2015; Rohmansyah et al., 2023). Moreover, HIIT is often perceived as more enjoyable than continuous training, despite similar RPE (Thum et al., 2017).

While eccentric HIIT, a novel combination of eccentric exercise and interval training, has shown promise, especially in terms of eliciting greater mechanical stimuli with lower cardiovascular strain, it may initially provoke muscle soreness, decrements in muscle function and longer recovery times compared to a work matched continuous training (Green et al., 2022; Lipski et al., 2018a). Nonetheless, evidence suggests that gradual exposure to eccentric loading fosters neuromuscular adaptations that attenuate the adverse effects (delayed onset muscle soreness (DOMS), decreased muscular function and range of motion, inflammatory episodes, swelling) over time (Hody et al., 2019; Nosaka et al., 2001). Eccentric HIIT thus represents a potential compromise between the high metabolic demands of concentric HIIT and the limited cardiovascular stimulus of continuous eccentric training (Peñailillo et al., 2023).

Given that eccentric cycling at a fixed workload elicits 40–80% lower oxygen consumption compared to concentric cycling (Barreto et al., 2021; P. C. LaStayo et al., 2003), combining eccentric loading with the interval format may provide a unique stimulus to enhance both aerobic and neuromuscular

adaptations. Furthermore, this modality may confer these benefits with lower perceived effort and cardiovascular strain, making it particularly relevant for elderly or clinical populations.

However, despite its theoretical advantages, comparative studies examining the acute and chronic effects of eccentric HIIT versus other training modalities remain scarce. In particular, no previous study has comprehensively assessed the physiological and perceptual responses to eccentric interval cycling relative to both continuous eccentric training and concentric HIIT under matched workload conditions.

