The 14-week training intervention was structured into three consecutive phases: (1) familiarization, (2) initial training, and (3) progressive training. All participants completed two supervised sessions per week, either on a recumbent eccentric ergometer (*Cyclus 2*, RBM Elektronik-Automation GmbH, Germany) or a seated concentric cycle ergometer (*Technogym*, Italy), depending on group allocation.

1. Phase 1 (T1) – Familiarization (Weeks 2–5)

During the familiarization phase, all groups completed work-matched sessions adapted to their respective contraction modality (eccentric or concentric cycling). Based on the findings of Lipski et al., a conversion ratio of 1.5 was used to estimate eccentric MAP (eMAP) from concentric MAP (cMAP), such that 100% eMAP was considered equivalent to 150% of cMAP.

Training intensity and duration were progressively increased across the four weeks. Participants began with 5 minutes of cycling at 30% of their cMAP and progressed to 30 minutes by the end of the phase. Final familiarization sessions were as follows:

- **Eccentric Continuous Group (EC):** 30 minutes (min) at 60% of cMAP
- **Concentric Interval Group (CI):** 9 x 2 min training/1 min rest at 65% of cMAP
- **Eccentric Interval Group (EI):** 9 x 2 min training/1 min rest at 100% of cMAP

This phase aimed to ensure adequate neuromuscular adaptation to the modality-specific demands and minimize potential DOMS, particularly in the eccentric groups.

2. Phase 2 (T2) – Initial Training (Weeks 6–9)

In the second phase, all groups trained at an intensity equivalent to 80% of their modality-specific MAP for 30 minutes per session:

- **EI Group:** 10 x 2 min training/1 min rest at 120% of cMAP
- **EC Group:** 30 min at 80% of cMAP
- **CI Group:** 10 x 2 min training/1 min rest at 80% of cMAP

3. Phase 3 (T3) – Progressive Training (Weeks 10–13)

Training intensity was further increased to 90% of each group's modality-specific MAP:

- **EI Group:** 10 x 2 min training/1 min rest at 135% of cMAP
- **EC Group:** 30 min at 90% of cMAP
- **CI Group:** 10 x 2 min training/1 min rest at 90% of cMAP

This progressive overload aimed to enhance aerobic capacity and muscular adaptations in a contraction-specific manner. All sessions remained isocaloric and time-matched across groups to allow for valid comparisons.

D. Training Parameters

1. Heart Rate Monitoring

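### Sessions are called isocaloric and time-matched across groups, but on the prescribed loads the concentric arm does two-thirds of the eccentric arms' mechanical work in Phases 2–3; what matches there is work relative to modality-specific MAP

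*Combined protocol and SAP*

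**What the plan says.** The training section (III.C) closes its description of the three phases with "All sessions remained isocaloric and time-matched across groups to allow for valid comparisons". Of Phase 1 it says: "During the familiarization phase, all groups completed work-matched sessions adapted to their respective contraction modality". It fixes the exchange rate between modalities, "such that 100% eMAP was considered equivalent to 150% of cMAP", where eMAP is eccentric and cMAP concentric maximal aerobic power. Of Phase 2 it says "all groups trained at an intensity equivalent to 80% of their modality-specific MAP for 30 minutes per session", and it gives 90% in the same way for Phase 3. The load of each arm is then listed as a percentage of cMAP.

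The Introduction uses matching language twice. Its gap statement refers to eccentric intervals "relative to both continuous eccentric training and concentric HIIT under matched workload conditions". Its aim calls only the continuous eccentric arm work-matched. The Introduction also reports 40–80% lower oxygen consumption for eccentric than for concentric cycling at a fixed workload, and it hypothesises that EI will give its benefits at a lower metabolic cost than CI.

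**The concern.** The closing sentence of III.C is the plan's stated reason for treating the arms as comparable. EI and CI have the same interval structure in Phases 2–3, but EI is set at 120% and 135% of cMAP and CI at 80% and 90%. Their mechanical work therefore cannot be equal.

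The EI versus CI contrast is one of the two that the plan hypothesises about, and isometric strength and MAP are the primary outcomes (II.B). A reader who accepts the sentence would attribute a difference in those outcomes to contraction mode at equal energy or equal work. The prescriptions do not support that attribution.

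**Working it through.** **Inputs.** Final Phase 1, Phase 2 and Phase 3 loads are from III.C.1 to III.C.3. Weeks 4–5 loads are from the Summary table. MAP in that table is taken as cMAP, because its last Phase 1 entries equal those in III.C.1. The load in rest minutes is not given; it is assumed to be zero and then varied.

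**Plan's own conversion.** 0.80 × 1.5 = 120% and 0.90 × 1.5 = 135% of cMAP. These reproduce the EI loads.

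**Absolute work** = loaded minutes × fraction of cMAP, in cMAP-min per session:

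| Session | EI | EC | CI | CI/EI |
|---|---|---|---|---|
| Last of Phase 1 | 18 × 1.00 = 18 | 30 × 0.60 = 18 | 18 × 0.65 = 11.7 | 0.65 |
| Phase 2 | 20 × 1.20 = 24 | 30 × 0.80 = 24 | 20 × 0.80 = 16 | 0.667 |
| Phase 3 | 20 × 1.35 = 27 | 30 × 0.90 = 27 | 20 × 0.90 = 18 | 0.667 |

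These are ratios per session, so they do not depend on the number of sessions per week.

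**Sensitivity to rest load (Phases 2–3).** Put the same active rest, 10% to 30% of cMAP, into the 10 rest minutes of EI and CI. This adds 1 to 3 cMAP-min to each.

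- Phase 2 CI/EI: 17/25 = 0.68 to 19/27 = 0.70.
- Phase 3 CI/EI: 19/28 = 0.68 to 21/30 = 0.70.
- EI then exceeds EC by 4% (28/27) to 13% (27/24), so equality of EI and EC requires unloaded rest.

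**Relative work** = absolute work ÷ 1.5 for EI and EC, ÷ 1 for CI:

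- Phase 2: 24/1.5 = 16, 24/1.5 = 16, 16.
- Phase 3: 27/1.5 = 18, 27/1.5 = 18, 18.
- Last Phase 1 session: 12, 12, 11.7.

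In the four weeks 4–5 sessions, relative work is:

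- EI: 4.8, 6.4, 9.6, 12.0.
- EC: 5.33, 6.67, 10.0, 12.0.
- CI: 4.8, 6.0, 9.0, 11.7.

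EC is 11% above CI in three of the four. Matching on relative work is exact in Phases 2–3 and approximate in Phase 1.

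**Metabolic energy.** Sessions cannot use equal energy by design while EI is expected to cost less than CI. The 40–80% figure points the same way. If cost were proportional to load (assumption), EI at 1.5 times CI's load would cost the same only with a reduction of 1 − 1/1.5 = 33.3%, which is below that range. The figure is for a fixed workload, so it is used here for direction only. Between EI and EC the plan expects a similar metabolic load, so the conflict concerns CI.

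**Intensity of EC.** 80/150 = 53.3% and 90/150 = 60% of eMAP, not 80% and 90%.

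**Session time.** In Phases 2–3 the interval arms take 10 × 3 = 30 minutes, the same as EC. In the last Phase 1 session they take 9 × 3 = 27 minutes against 30. In the first two weeks 4–5 sessions they take 6 × 3 = 18 against 20.

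**The case against.** The strongest reply is that *isocaloric* is a loose word for a coherent design. The 1.5 conversion, the references to modality-specific MAP and the Phase 1 phrase about adapting sessions to the modality all point to relative matching. Every load is printed in cMAP just above the disputed sentence, and the aim calls only EC work-matched. Matching CI to EI on absolute work would need CI intervals at 24/20 = 120% and 27/20 = 135% of cMAP, above concentric maximal aerobic power. The EI versus CI hypothesis, benefit at lower cost, is itself a comparison of programmes.

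Most of this stands. The design is sensible, and the plan comes close to describing it. But equal relative work is not equal energy, the sentence claims the latter, and it does so to justify the comparisons. No sentence says that work per session is equalised relative to modality-specific MAP. The gap statement in the Introduction also extends matched workload to CI.

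A reader might infer from the intensity error that EC is under-dosed. It is not. The session average is 53% and 60% of modality-specific MAP in every arm: 80% × 20/30 and 90% × 20/30 in EI and CI, and continuously in EC. The likely slip is that EC's percentages are of cMAP while the sentence says modality-specific MAP.

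A reader might also object that weeks 2–3 are not labelled by arm in the Summary table. That may come from how the table was extracted, and nothing here relies on it.

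**Conclusion.** The statement is wrong as written. With rest unloaded, CI does 66.7% of the absolute work of EI and EC in Phases 2–3 and 65% in the last Phase 1 session. Equal active rest up to 30% of cMAP moves CI/EI in Phases 2–3 only to about 0.70. As a claim about metabolic energy, it contradicts the plan's own hypothesis. *Time-matched* holds in Phases 2–3 but not in the last Phase 1 session. The stated EC intensity is wrong.

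A reader might go further and infer that the between-group comparisons are invalid. The documents do not support that: allocation is random, and the tests do not depend on equal energy. The limit is on interpretation. EI and CI are matched in Phases 2–3 on session time and relative work, with about 1.5 times the absolute work in EI. A difference between them is therefore between programmes and cannot be attributed to contraction mode at equal work or energy. EI versus EC is not affected in this way if rest is unloaded.

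**What to change.** - Delete *isocaloric* from III.C.
- State that Phases 2–3 are matched on session time and on work relative to modality-specific MAP, and that Phase 1 is matched only approximately on both.
- Give the load in the rest minutes, and state that EI and EC have equal absolute work in Phases 2–3 if that load is zero.
- Correct EC's intensity to 53% and 60% of eMAP (80% and 90% of cMAP).
- State that EI does about 1.5 times CI's absolute work, so an EI versus CI difference is between programmes and not an effect of contraction mode at equal work or energy. Align the matched-workload phrase in the Introduction with this.

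The cost is a few sentences in Sections I and III.C. Randomisation, outcomes, sample size and tests do not change. The price is a weaker, but correct, claim for EI versus CI.

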The present study aims to compare the acute and training responses of (1) eccentric high intensity interval training, (2) work-matched continuous eccentric training, and (3) concentric high intensity interval training, all performed on cycle ergometers. The variables of interest include ratings of perceived exertion (RPE), cognitive demand (Fat), heart rate (HR), maximal oxygen consumption ($VO_{2\text{max}}$), maximal aerobic power (MAP), and various functional and health-related parameters.

It is hypothesized that eccentric HIIT will produce comparable or superior improvements in functional outcomes relative to concentric HIIT, but at a lower metabolic and perceptual cost. Furthermore, eccentric HIIT is expected to yield greater physiological benefits than continuous eccentric training for a similar perceived and metabolic load.

II. Population

A. Recruitment

The study was conducted on sedentary individuals aged 50–75, engaging in no more than 3 hours of light-to-moderate activity per week.

Participants were recruited through:

- Notices in the Movement Sciences Department (ULiège, Blanc-Gravier),
- Social media,
- Professional/personal networks.

All participants are legal adults, volunteers, and signed an informed consent form, previously approved by the University Hospital Ethics Committee of Liège (ref 2023/072).

B. Sample Size Estimation

Given the study design (three groups, two time points), a repeated-measures ANOVA was selected to assess within-group changes, between-group differences, and potential group \times time interactions. The primary outcomes were changes in isometric maximal strength and maximal aerobic power. The significance level (α) was set at 2.5% to account for multiple primary comparisons.

Assuming a moderate to large effect size ($f = 0.3\text{--}0.5$) and a statistical power of 80%, the required total sample size was estimated to range from $n = 18$ to $n = 36$. Accounting for an anticipated dropout rate of 20%, the recommended sample size ranged from 8 to 15 participants per group. Sample size calculations were performed using *G*Power* software.

Inclusion criteria:

- Aged 55 to 75 yo;
- Sedentary or engaging in <3h of regular physical activity/week.

Exclusion criteria:

- Smoking;
- Recent lower limb injury or pain (past 6 months) interfering with ergocycle tests;
- Uncontrolled acute or chronic disease;
- Cardiovascular disorders.

III. Experimental Protocol

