This is a **prospective interventional longitudinal study**, conducted during a single period (year 2024 - 2025).

The experimental study will compare the effects of:

- Two **eccentric training protocols** (continuous or interval training),
- One **concentric training protocol**, all using ergometric bikes.

Random assignment will place subjects into one of three experimental groups. They will follow a 14-week training program with 2 sessions/week (total 28 sessions). Participants must abstain from physical activity the week before and during the entire protocol.

Symptomatic management techniques are prohibited. Various parameters will be assessed before, during, and after the program to compare the protocols.

A. Experimental Design

Participants in the EI and EC groups trained using an eccentric ergometer, while the CI group trained on a concentric ergometer. Baseline and post-intervention assessments were conducted during weeks 1 and 14, respectively. These included a maximal incremental cycling test to determine maximal oxygen consumption and maximal aerobic power, followed by six functional performance assessments.

The training protocol consisted of three consecutive 4-week phases:

1. Familiarization Phase (Weeks 2–5)
2. Initial Training Phase (Weeks 6–9)
3. Progressive Training Phase (Weeks 10–13) with increased training intensity.

B. Incremental Cycling Test

At the first and final visits, participants underwent a concentric incremental cycling test to determine maximal oxygen consumption and maximal aerobic power. The test began with a standardized 2-minute warm-up at 30 watts (W) and a cadence of 60 revolutions per minute (rpm). The workload was then increased every minute by 15 W for women and 20 W for men until volitional exhaustion.

Participants were instructed to maintain a cadence above 60 rpm and were verbally encouraged throughout the test. Respiratory gas exchange, heart rate and blood lactate concentration (sampled every 2 minutes) were continuously monitored. The test was considered maximal if one or more of the following criteria were met:

- Plateau in VO_2 despite increasing workload,
- Respiratory quotient (RQ) > 1.1 ,
- HR $> 85\%$ of age-predicted maximum,
- Blood lactate concentration $> 4 \text{ mmol/L}$,
- Inability to maintain the target cadence.

C. Training Protocol

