Throughout each training session, HR was continuously monitored using a *Polar Verity Sense optical heart rate sensor* (*Polar Electro Oy, Finland*), worn on the upper arm and connected to the *Polar Flow* application via an *Apple iPad*. Both mean and maximal HR (mean HR and max HR) values were recorded per session. They are expressed in percentage of the maximal HR measured during the incremental cycling test (% max HR). For analysis, mean and max HR values were averaged for each of the three training phases.

2. Rating of Perceived Exertion

At the end of each training session, participants reported their RPE using the Borg RPE scale, ranging from 6 (no exertion) to 20 (maximal exertion). Average RPE values were calculated for each training phase and used for subsequent analysis.

3. Cognitive Demand

Perceived Fat was assessed following each session using a modified Borg scale ranging from 0 (no cognitive effort) to 10 (maximal cognitive effort). Participants were asked to evaluate the mental demand specifically related to the cognitive focus required during training. Phase-wise averages were computed for analysis.

4. Perceived Muscle Soreness

Prior to each training session, participants rated their perceived muscle soreness in the lower limbs using a visual analog scale (VAS) ranging from 0 millimeters (mm) (no soreness) to 200 mm (unbearable soreness). These ratings were intended to reflect residual soreness from the previous session. Means of each training phase were computed for statistical analysis.

E. Functional Parameters

A battery of six functional tests was performed pre- and post-intervention to evaluate intra-group improvements and inter-group differences. All tests were administered by the same trained evaluator to minimize inter-rater variability. Standardized instructions and verbal encouragement were provided to ensure consistency across participants.

1. Maximal Isometric Force (MIF)

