Aerobic endurance was evaluated via the 6MWT. Participants were instructed to walk as far as possible in six minutes along a 30-meter indoor track, turning around two cones at either end. HR and RPE were monitored throughout the test. The total distance covered was expressed in meters.

F. Statistical Analyses

All statistical analyses were conducted using R Commander (R version 4.4.2; R Foundation for Statistical Computing, Vienna, Austria). Data were initially assessed for normality using the Shapiro–Wilk test and for homogeneity of variances using Levene's test. For normally distributed variables with equal variances, repeated-measures analysis of variance (ANOVA) was used to examine the effects of time (pre- vs. post-intervention), group (EI, EC, CI), and their interaction. When significant main effects or interactions were found, post hoc comparisons were performed using Tukey's Honestly Significant Difference (HSD) test to control for Type I error.

For outcome variables related to participants characteristics and functional performance that did not meet the assumptions of normality, non-parametric tests were applied. Specifically, within-group comparisons across time were conducted using the Wilcoxon signed-rank test, and between-group comparisons were evaluated using the Kruskal–Wallis test.

All results were considered statistically significant at $p < 0.05$. Data are presented as mean \pm standard deviation (SD) for parametric variables and as median with interquartile range (IQR) for non-parametric variables, unless otherwise stated.

Summary

Phase 0 – Testing	Week –1 (2 sessions)	Evaluation
Phase 1 – Familiarization	Week 2-3 (2x/wk)	5' 20% MAP - 10' 30% MAP 15' 30% MAP - 20' 40% MAP 5' 20% - 10' 20% 15' 30% - 20' 30%
	Week 4-5 (EC, 2x/wk)	20' 40 et 50 % MAP, 60 rpm 30' 50 et 60% MAP, 60 rpm
	Week 4-5 (EI, 2x/wk)	6 x 2'-1' à 60 et 80% MAP, 60 rpm 9 x 2'-1' à 80 et 100% MAP, 60 rpm
	Week 4-5 (CI, 2x/wk)	6 x 2'-1' à 40 et 50% MAP, 60 rpm 9 x 2'-1' à 50 et 65% MAP, 60 rpm
Phase 2 – Training	Week 6-9 (EC, 3x/wk)	30' 80% MAP, 60 rpm
	Week 6-9 (EI, 3x/wk)	10 x 2'-1' 120% MAP, 60 rpm
	Week 6-9 (CI, 3x/wk)	10 x 2'-1' 80% MAP, 60 rpm
Phase 3 – Training	Week 10 – 13 (EC, 3x/wk)	30' 90% MAP, 60 rpm
	Week 10 – 13 (EI, 3x/wk)	10 x 2'-1' 135% MAP, 60 rpm
	Week 10 – 13 (CI, 3x/wk)	10 x 2'-1' 90% MAP, 60 rpm
Phase 4 – Retesting	Week 14	Evaluation

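### All three arms train, so the planned time-effect and within-arm tests cannot separate training gains from practice on the tests

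*Combined protocol and SAP*

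**What the plan says.** Section III states: "Random assignment will place subjects into one of three experimental groups". Section III.A describes what each arm does: "Participants in the EI and EC groups trained using an eccentric ergometer, while the CI group trained on a concentric ergometer". All three arms therefore receive an active programme. The same section gives the timing of the tests: "Baseline and post-intervention assessments were conducted during weeks 1 and 14, respectively".

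Within-arm change is a planned target of inference in three places:

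- II.B (Sample Size Estimation): "a repeated-measures ANOVA was selected to assess within-group changes, between-group differences", and the group-by-time interaction.
- III.E (Functional Parameters): "A battery of six functional tests was performed pre- and post-intervention to evaluate intra-group improvements and inter-group differences".
- III.F (Statistical Analyses): the ANOVA tests time, group and their interaction, with Tukey comparisons after any significant effect. For non-normal participant characteristics and functional outcomes, "within-group comparisons across time were conducted using the Wilcoxon signed-rank test", and arms are compared by Kruskal-Wallis. The level is 0.05 throughout.

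No section limits what a significant time effect or within-arm test may be said to show.

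**The concern.** Randomisation protects contrasts between arms. It does not protect the change from week 1 to week 14 inside one arm, or the average of that change over arms. Someone who meets the balance test, the timed tests or an exhaustive cycling test for the second time may do better because the test is familiar. With no untrained arm, delayed start or repeated baseline, the plan cannot tell that gain from a training gain.

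The familiarisation phase in III.C does not help here: it adapts participants to the training modality, not to the outcome tests.

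This touches the hypothesis directly. The introduction expects eccentric interval training to do at least as well as concentric interval training on functional outcomes. If training did nothing and practice helped all arms equally, the result would be a significant time effect with no interaction. That pattern could be read as three programmes that work about equally well.

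The non-parametric route is the more exposed. III.F does not say that Kruskal-Wallis is applied to change scores, so on that route the only test explicitly of change is the within-arm one.

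**Working it through.** **Inputs from the documents.** Three arms, two time points, total N of 18 to 36, effect size f = 0.3 to 0.5, power 80%, dropout 20% and a sizing level of 0.025 (all II.B); analysis level 0.05 (III.F).

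**Assumptions.** Equal arms, two-sided tests, correlation ρ = 0.5 between time points, no training effect, and the same practice gain d in every arm, measured in SD of the pre-post change. The documents give no value for d, so a range is shown.

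**1. The plan's own sample size.** For the group-by-time interaction, λ = f²·N·m/(1 − ρ), with m = 2 and degrees of freedom 2 and N − 3.

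- f = 0.3, N = 36: λ = 0.09 × 36 × 2 / 0.5 = 12.96; power at 0.025 is 0.803.
- f = 0.5, N = 18: λ = 0.25 × 18 × 2 / 0.5 = 18; power is 0.879.
- Dropout: 36/0.8 = 45, or 15 per arm; 18/0.8 = 22.5, or 7.5 per arm, rounded up to 8.

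This matches the stated 18 to 36 in total and 8 to 15 per group. Sizing for the time effect would give 30 and 15, and for the between-group effect 102 and 39. Under ρ = 0.5, the stated N is therefore the N for the interaction.

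**2. Time main effect under practice alone.** λ = N·d², with degrees of freedom 1 and N − 3, level 0.05.

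| d (assumed) | λ at N = 36 | significant, N = 36 | significant, N = 18 |
|---|---|---|---|
| 0 | 0 | 5% | 5% |
| 0.2 | 1.44 | 21% | 13% |
| 0.3 | 3.24 | 42% | 22% |
| 0.5 | 9.00 | 83% | 51% |

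**3. Wilcoxon test in one arm of 12.** By simulation with normally distributed changes (4,000 trials), a significant change in the favourable direction appears in 1.9% of arms at d = 0, 13.3% at 0.3 and 31.5% at 0.5. At least one of the three arms shows it in 35% and 68% of trials at 0.3 and 0.5. A separate run of 20,000 trials gave 13.4% and 31.6% for one arm.

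**4. Tukey comparisons on the ANOVA route.** III.F does not define the family. If it is all six group-by-time cells with the pooled within-subject error and 12 per arm, one arm is declared improved in about 3% of trials at d = 0.3 and 12% at 0.5.

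**5. Between-arm test of change.** With two time points the interaction is equivalent to a one-way ANOVA on the changes. In the 4,000 simulated trials it rejected in 5.3%, 5.0% and 4.3% at d = 0, 0.3 and 0.5. In the 20,000-trial run, Kruskal-Wallis on change scores rejected in 4.6%, 4.8% and 4.9%. A gain shared by all arms cancels.

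**The case against.** The strongest reply is that this is a comparative trial. Its stated aim and both hypotheses compare arms, the interaction is planned, and the sample size reproduces as an interaction calculation. All of that stands. A reader might infer that the randomised comparison is itself compromised; the documents do not support that, because a practice gain common to all arms drops out of it.

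The plan also contains real safeguards. The isometric force test has a warm-up, three submaximal contractions and the best of five efforts. Handgrip, sit-to-stand and timed up-and-go keep the best of three. One evaluator gives standardised instructions, and about 13 weeks separate the assessments. The Summary table lists two sessions in the first testing week. These reduce learning within a visit but do not exclude learning between visits, and no repeat is stated for the balance test, the six-minute walk or the incremental test. The two sessions are labelled only as evaluation. If one was a practice run, the concern would shrink, and the plan should say so.

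Three further readings go too far:

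- Regression to the mean and encouragement might be added as causes. Eligibility is by age, activity, smoking, injury and disease, not by a baseline test score. Encouragement is described as standardised, with no difference between visits. Neither has much support in the text.
- One might quote an ordinary paired t-test in one arm of 12, which gives 16% and 35% at 0.3 and 0.5 SD. The plan contains no such test; the planned procedures give the lower figures above.
- One might predict that the report will lead with time effects. That is a forecast. The documents show only that nothing prevents it.

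**Conclusion.** The concern holds for the time main effect and the within-arm tests, and only for those. Followed as written, the plan can declare improvement in an arm, or in all arms together, that the design cannot attribute to training.

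The size depends on the unknown practice effect. At 0.2 SD of change and N = 36 the time effect is already significant about four times as often as the nominal 5% (21%). The percentages describe a range under assumed practice gains and zero training effect; they are not an expected error rate for this trial. They also use the 0.05 level of III.F, and would be lower at the 2.5% of II.B. The conclusion that within-arm change is not attributable to training does not depend on the percentages. The near-5% behaviour of the between-arm test does depend on the practice gain being equal across arms.

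**What to change.** In III.E and III.F, state that efficacy conclusions rest on between-arm differences in pre-post change. Name the test for both routes: the group-by-time interaction where the ANOVA assumptions hold, and Kruskal-Wallis applied to change scores where they do not.

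Report each arm's mean or median change with a confidence interval as descriptive, with a sentence saying that it cannot be separated from practice and other time effects. Add that similar within-arm gains are not to be read as showing comparable training effects. If either session in the first testing week included a practice run of the outcome tests, say so.

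No new data and no larger sample are needed, since the stated N is already the one for the interaction. The change is more than a caveat on the non-parametric route, where the between-arm analysis of change has to be specified. The trial gives up per-arm efficacy claims, which II.B and III.E now list as a purpose.

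### A Shapiro–Wilk/Levene pretest, not fully specified, chooses the analysis of both primary outcomes, and leaves maximal aerobic power (if non-normal) and any unequal-variance outcome without a clearly assigned test

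*Combined protocol and SAP*

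**What the plan says.** Section II.B (Sample Size Estimation) names two primaries: "The primary outcomes were changes in isometric maximal strength and maximal aerobic power". It ties the sizing to one method: "Given the study design (three groups, two time points), a repeated-measures ANOVA was selected". Alpha "was set at 2.5% to account for multiple primary comparisons", with "a statistical power of 80"%, a Cohen f of 0.3 to 0.5, a total of 18 to 36, and 8 to 15 per group after a 20% dropout allowance.

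Section III.F (Statistical Analyses) then makes the method conditional. "Data were initially assessed for normality using the Shapiro–Wilk test", and variances are checked with Levene's test. The ANOVA with time, group and their interaction is for variables that pass both. The only other route reads: "For outcome variables related to participants characteristics and functional performance that did not meet the assumptions of normality, non-parametric tests were applied". It consists of Wilcoxon signed-rank tests within groups and Kruskal–Wallis tests between groups.

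Sections III.A and III.B place MAP and VO2max in the incremental cycling test. Section III.A lists that test apart from the six functional assessments. Section III.E describes those six; isometric force is the first, and MAP is not among them.

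**The concern.** The primary analysis should be fixed before the outcome data are seen. Here a preliminary test on small arms picks it, and the decision tree has three weaknesses.

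- **The gate is not fully specified.** The plan does not say what is tested, in which subsets, or at what level. Two analysts who both follow III.F could take different branches with the same data.
- **The fallback does not clearly reach MAP.** It is worded for participant characteristics and functional performance. MAP belongs to the incremental test.
- **Unequal variances lead nowhere.** Only non-normality triggers the fallback. An outcome that is normal but fails Levene is excluded from the ANOVA and sent to nothing. This applies to isometric strength as well.

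At stake is whether each primary outcome has one defined analysis, and whether the power statement in II.B describes the test that is run.

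**Working it through.** **1. Which test the sample size matches.** Inputs from II.B: 3 groups, 2 time points, f = 0.3 to 0.5, alpha 0.025, power 80%. The pre–post correlation is not given; 0.5 is assumed. For the group-by-time interaction, λ = f² × N × 2 / (1 − ρ), with 2 and N − 3 degrees of freedom.

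- f = 0.3, N = 36: λ = 0.09 × 36 × 2 / 0.5 = 12.96; power 80.3%.
- f = 0.5, N = 18: λ = 0.25 × 18 × 2 / 0.5 = 18; power 87.9%. This is the smallest N with equal groups (16 would do without balance).
- Dropout: 18 / 0.8 = 22.5, or 7.5 per group, so 8; 36 / 0.8 = 45, or 15 per group.

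The plan's figures reproduce. With the same alpha and correlation, the time main effect would need 30 and 15 in total, and the group main effect 102 and 39. The sizing therefore matches the group-by-time ANOVA.

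**2. Arm sizes at analysis.** Recruitment is 8 to 15 per group. After 20% dropout this is 8 × 0.8 = 6.4 to 15 × 0.8 = 12, so 6 to 15 covers the range.

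**3. How often the gate diverts an outcome that meets every assumption.** If k independent tests are each run at 0.05, the chance of at least one rejection is 1 − 0.95^k. The tests are not all independent, so this was also simulated with exactly normal, equal-variance data: 6 to 15 per arm, pre–post correlation 0.5 to 0.95, 1,500 to 6,000 runs per setting, Levene centred at the median. The 0.05 level is assumed from the general significance rule in III.F.

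| Reading of the pretest | Tests | If independent | Simulated |
|---|---|---|---|
| One Shapiro–Wilk on within-arm residuals of change | 1 | 5.0% | 4–6% |
| Shapiro–Wilk pooled over arms, at each time point | 2 | 9.8% | 8–12% |
| Shapiro–Wilk on change, in each arm | 3 | 14.3% | 12–16% |
| Shapiro–Wilk in all six group-by-time cells | 6 | 26.5% | 21–28% |
| Six cells plus Levene at each time point | 8 | 33.7% | 25–33% |

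Adding Levene raises every reading. With 8 per arm and correlation 0.5, the residual reading goes from 4.7% to 8.0%, pooled by time from 9.7% to 15.7%, change per arm from 14.2% to 17.2%, and six cells from 27.5% to 32.4%.

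**4. Where each outcome goes under III.F as worded.**

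| Pretest result | Isometric strength | MAP |
|---|---|---|
| Normal, equal variances | ANOVA | ANOVA |
| Non-normal | Wilcoxon / Kruskal–Wallis | No clearly assigned analysis |
| Normal, unequal variances | None given | None given |

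Even where the fallback applies, the Wilcoxon tests work within arms, and the plan does not say whether Kruskal–Wallis is run on change. Unless it is, neither addresses the group-by-time question sized in step 1.

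**The case against.** The strongest reply is that III.F says only that data were assessed. A reader might infer a test of raw values in every cell, and hence that about a quarter of sound outcomes are diverted. The documents do not support that as an unconditional statement: II.B defines the primaries as changes, so testing changes is at least as natural, and that gives 12–16% per arm or 4–6% on pooled residuals. This stands. The figure has to be given as a range that depends on the reading.

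A reader might also infer that choosing the test from the data inflates type I error. That has not been shown. When the six-cell gate was followed by either an ANOVA or a Kruskal–Wallis test, both on change, the simulated two-stage error was 4–6% at a nominal 5%. That check assumes Kruskal–Wallis is run on change, which the plan does not state.

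Two other extensions lack support. Combining the two primaries into one probability of diversion needs their dependence, which is not given. Arguing that a mixed-sex sample makes raw values fail needs a sex mix and a sex difference, and neither is given.

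On MAP, the fallback wording may be loose shorthand for all pre/post variables, as opposed to the session measures averaged over three phases, and participant characteristics could be meant to include baseline MAP. That is possible, so it is too strong to say that MAP certainly has no analysis. But the primary is the change in MAP, and III.A separates it from the functional tests; on the natural reading it is not covered. The unequal-variance gap does not depend on this wording.

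**Conclusion.** The concern holds as a fault of specification that should be fixed. Four things follow from the text without simulation: a pretest selects the method for both primaries, its operation is not fully specified, MAP has no clearly assigned analysis if non-normal, and no outcome has one if it is normal with unequal variances. A diverted primary is no longer analysed by the group-by-time ANOVA that 18–36 participants in total (8–15 per group) matches, and the two co-primaries may end up with different methods.

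The size is conditional. For ideal data the diverted share is about 4–6% at the low end and 21–28% for six cells, up to about 33% with Levene. This rests on tests at 0.05, 6–15 per arm and correlations of 0.5–0.95, none of which the plan states except the recruited group sizes and dropout rate behind the 6–15. The match to the sample size rests on an assumed correlation of 0.5. The documents do not show that the trial's error rate is wrong because of this rule.

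**What to change.** In III.F:

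1. Remove Shapiro–Wilk and Levene as a gate.
2. Pre-specify one analysis for both isometric strength and MAP: the between-arm comparison of change (the group-by-time term), used whatever the distribution checks show.
3. Use plots of the model residuals as description only.
4. Name one sensitivity analysis of the same contrast, for example a permutation p-value or heteroscedasticity-robust standard errors, and list isometric strength, MAP and VO2max as covered by it.

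This closes the MAP and unequal-variance gaps together and keeps the primary analysis on the test that the sample size matches. The choice between a permutation and a robust version is a matter of preference; naming one in advance is what counts. The cost is SAP wording and one extra run per outcome, with no new data.
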